4.3. Sample Size

Approximately 148 subjects will be enrolled in 4 cohorts (3 cohorts of SKI-O-703 and 1 cohort of placebo). Each cohort will consist of at least 37 subjects.

The study is powered to detect a difference of 0.8 in mean change from baseline to Week 12 in DAS28-hsCRP score between one of the groups treated with SKI-O-703 and the group treated with placebo. At least 37 subjects on a course of SKI-O-703 treatment are required to complete the study to show a change from baseline to Week 12 of 0.80 and higher as statistically significant with a power of 0.80 at the significance level of 0.05, using a 1-way analysis of variance and assuming a standard deviation of 1.25, compared with in the placebo group. Sample size determinations were based on the 4-component DAS28 and are likely to be similar with the 3-component DAS28 with fewer variables.

Given the 1:1:1:1 ratio of SKI-O-703 100 mg BID, 200 mg BID, 400 mg BID to placebo allocation, at least 37 subjects in each treatment group are required to complete the study, therefore at least 148 subjects need to be enrolled and randomized in the study. Assuming a drop-out of rate of 10%, up to 20 additional subjects may be enrolled to achieve the target number of subjects required to complete the study.

4.4. Randomization, Stratification, and Blinding

Subjects will be randomized using a permuted block randomization in parallel in a 1:1:1:1 ratio (37 subjects per group) to receive SKI-O-703 100 mg BID, 200 mg BID, 400 mg BID, or matching placebo. An interactive voice or web response system (IxRS) will be used to administer the randomization schedule. The randomization schedule will be stratified by prior anti-TNF α biologic agents use (Yes or No), number of previous csDMARDs treatments (0-2, ≥ 3), and specific geographic region (APAC, EMEA and NA).

This study is double-blind study. Neither the subjects nor the investigator will be aware of the treatment assignment for the subjects in each cohort. The study drugs will be similar in number and appearance for each cohort to maintain the study blind. Blinding will be maintained throughout the study until the final database lock.

4.5. Analysis Sets

The following analysis sets will be used:

Safety set: The Safety set is defined as all subjects who receive at least one dose of study drug (SKI-O-703 or placebo). Subjects will be analyzed as treated. This population will be used for summaries of safety data.

Intent-to-Treat (ITT) set: The ITT set is defined as all randomized subjects who receive at least one dose of study drug (SKI-O-703 or placebo). Subjects will be analyzed as randomized. This population will be used for all efficacy analyses and summaries of demographics and baseline characteristics data.

Modified Intention-to-Treat (mITT) set: The mITT set is defined as all the subjects who receive at least one dose of study drug (SKI-O-703 or placebo) and have at least 1 postbaseline assessment. Subjects will be analyzed as randomized. This population will be used for efficacy summaries and will include imputed data for subjects who withdraw from the study prior to the Week 12 visit.

Per Protocol (PP) set: The PP set is defined as all the subjects in ITT set who don't have any major protocol deviation(s) which will be flagged in the protocol deviation list and be compliant with the treatment as defined in [Section 7.2.2](#). All the efficacy analyses will be repeated on PP set. Subjects will be analyzed as randomized.

Pharmacokinetic (PK) set: The PK set will consist of all subjects who receive SKI-O-703 and have at least 1 measurable plasma concentration. Subjects who have partial data and/or major protocol deviations that may impact PK, and subjects who experience emesis, will be evaluated on a case-by-case basis and may be excluded from the PK population. This population will be used for summaries of PK data.

Pharmacodynamic (PD) set: The PD set will consist of all subjects who receive at least 1 dose of study drug (SKI-O-703 or placebo) and have at least 1 evaluable postdose PD value. Subjects who have partial data and/or major protocol deviations that may impact PD will be evaluated on a case by case basis and may be excluded from the PD population. This population will be used for summaries of PD data

Pharmacokinetic (PK)/pharmacodynamic (PD) set: The PK/PD set will consist of all subjects included in both the PK and PD populations. This population will be used for the PK/PD analyses.

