On Day 1, the subject should complete the Patient's Global Assessment of Disease Activity, the Patient's Assessment of Pain, and the Health assessment questionnaire before site personnel perform any clinical assessments. These should also be completed before any interaction with site personnel has occurred to avoid biasing the subject's response. After that subject's eligibility will be confirmed and baseline safety evaluations will be performed (12-lead ECG, physical examination, vital sign measurements, weight, urine pregnancy test, and safety laboratory assessment). Following predose study procedures, the subject will be randomly assigned to receive either SKI-O-703 or placebo. On Day 1, subject will be administered his/her first dose of study medication no later than 30 minutes after food with approximately 8 ounces (240 mL) of water by the site personnel. The study site personnel will check the subject's mouth to ensure the study drug and entire volume of water was swallowed.

A subset of subjects from each cohort who provide additional consent will be subjected to additional PK and PD assessments according to the Schedule of Events (Table 6-1). Due to PD assay limitations, PK and PD sampling will only be performed at selected sites that are deemed suitable to support PK/PD assessment (ie, which are within an acceptable shipping distance from a PD laboratory). Every effort will be made to achieve a minimum of 24 subjects (6 subjects per treatment group) in the PK/PD subgroup. It is important to note that there is no upper limit to the number of subjects that will be enrolled to the PK/PD subgroup in any region (as many subjects will be assigned to the PK/PD subgroup as is practical), and the number of subjects does not need to be identical between treatment groups; however, every effort will be made to ensure that the number of subjects enrolled to each treatment group is similar.

The second dose will be administered approximately 12 hours (± 2 hours) after the first dose. The second dose and all subsequent doses will be self-administered by the subject. The subjects will be instructed to take study medication no later than 30 minutes after food.

12-week Treatment Period

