11.3. Pharmacodynamic Parameters

The following PD parameters will be estimated on Day 1 and 84 using change from baseline in activated CD63+ basophils in peripheral blood using actual sampling times via non-compartment analysis using Phoenix WinNonlin version 6.4 or higher:

E_{max} Maximum effect

TE_{max} Time to achieve maximum effect

AUEC_{0-tau} Area under the effect versus time curve within a dosing interval

Actual PK blood sampling times will be used for the assessment of all PD parameters, and negative baseline-adjusted values will be included in the analysis.

PD parameters will be presented in data listings and summarized separately using the following descriptive statistics for each treatment and analyte (n, mean, SD, CV, minimum, median, and maximum). For TE_{max} , only n, median, minimum and maximum will be reported.

12. Pharmacodynamic/Pharmacokinetic Analysis

The PK/PD relationship between SKI-O-592, M2, and M4 and CFB in percent of activated CD63+ basophils will be assessed. Scatter plots of individual plasma concentrations of SKI-O-592, M2, and M4 will be presented versus individual change from baseline in percentage of activated CD63+ basophils.

In addition, the relationship between individual concentrations of SKI-O-592, M2, and M4 and individual CFB in percent of activated CD63+ basophils will be modelled using an E_{max} model. If the data warrant, the model will be a nonlinear mixed effect model with inter-individual variability considered for the parameters in the model. If convergence is not obtained with the E_{max} model, the E_{max} parameter may be fixed (assuming 100% reduction is possible) or a linear model will be considered. The parameter estimates for the model will be presented.

13. Interim Analysis

No interim analysis is planned in this study.

14. Changes in the Planned Analysis

No changes.

15. Appendices

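### The basophil concentration–response model has no term for non-drug change by Week 12, and the PK/PD set omits the placebo subjects who could anchor one

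*SAP*

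**What the plan says.** **Who is sampled.** Protocol 3.1 and SAP 3.1 plan serial PK and PD sampling in a subset of every treatment group, placebo included: "Every effort will be made to achieve a minimum of 24 subjects (6 subjects per treatment group) in the PK/PD subgroup".

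**Who is analysed.** SAP 4.5 defines three sets, and Protocol 7.5 matches it:
- PK set: "The PK set will consist of all subjects who receive SKI-O-703 and have at least 1 measurable plasma concentration".
- PD set: anyone dosed with SKI-O-703 or placebo who has an evaluable postdose PD value.
- PK/PD set: "The PK/PD set will consist of all subjects included in both the PK and PD populations". On its use, SAP 4.5 adds: "This population will be used for the PK/PD analyses".

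**What is fitted.** Protocol 7.7.8 makes PK/PD modelling optional and leaves the details to the SAP. SAP Section 12 says that the relationship between individual concentrations and "individual CFB in percent of activated CD63+ basophils will be modelled using" an Emax model, with inter-individual variability if the data allow. If the fit does not converge, the Emax "parameter may be fixed (assuming 100% reduction is possible) or a linear model will be considered". No equation is given. No intercept, placebo, time or day term is named, and the SAP does not say whether Day 1 and Week 12 are fitted together.

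**Baseline.** SAP 11.1 takes the Day 1 predose sample as the PD baseline.

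**The concern.** The endpoint in SAP 3.2.3 covers Day 1 and Week 12. Over 12 weeks the percentage of activated basophils could move for reasons other than drug, such as disease course, assay drift or regression to the mean. The plan contains one possible source of the last: SAP 11.1 drops subjects whose single predose value is below the limit of detection. Selecting on one noisy value tends to produce an apparent later fall in every arm, of unknown size.

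In an active subject, the one assured drug-free record is the Day 1 predose sample. There, change from baseline is zero by construction, so it carries no information about drift. Every other active record comes after dosing. A model with concentration as its only explanatory variable must absorb any common shift into Emax, into EC50 (the only place left if Emax is fixed), or into the slope of the linear fallback. What is at stake is the reported size and shape of the concentration–effect relationship.

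**Working it through.** **1. Set sizes.** The planned subgroup is 4 groups × 6 = 24, which reproduces the stated minimum. Under the definitions the PK/PD set holds 3 × 6 = 18, so 6 of 24 (25%) are left out. All six are placebo. (A placebo subject given SKI-O-703 in error could enter; this is trivial.)

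**2. Why placebo rows alone do nothing.** Without a drift term the model is

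CFB = −Emax × C / (EC50 + C).

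At C = 0 this is 0 for any Emax and EC50. In a least-squares fit, placebo rows therefore add a constant to the sum of squares and leave both estimates where they were. A straight line through the origin behaves the same way.

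**3. Share of drift credited to drug, by hand.** Suppose there is no drug effect, a shift of −d at Week 12 only, and non-zero concentrations after the first dose. The SAP 11.2 PD schedule gives 6 postdose records on Day 1 and 7 records on Day 84 per subject. The fitted curve is then roughly flat at the mean of those 13 records:

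- Days pooled: (6 × 0 + 7 × d) / 13 = 0.54 d. For d = 10 points this is 5.4.
- Week 12 alone: (7 × d) / 7 = d.
- Days pooled with the Week 2, 4 and 8 troughs, and drift rising linearly: (2/12 + 4/12 + 8/12 + 7) d / 16 = 8.17 d / 16 = 0.51 d.

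**4. Simulation separating the two changes.** Assumed inputs: 6 per arm, residual SD 4 points, Emax 20, EC50 300 ng/mL, elimination rate 0.2 per hour, drift 10 points at Week 12, 200 runs, days pooled. Exposure is scaled to the AUC of 14600 h·ng/mL predicted for 400 mg BID in Protocol 1.3. The true effect at C = 1000 ng/mL is 20 × 1000 / (300 + 1000) = 15.38. Median estimated effect at that concentration:

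| Fit | No true effect | True effect 15.38 |
|---|---|---|
| Active arms, no day term | 5.42 | 20.68 |
| Placebo at C = 0 added, no day term | 5.42 | 20.68 |
| Active arms, day term | 0.09 | 15.37 |
| Placebo added and day term | 0.08 | 15.42 |

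The excess with a true effect is 20.68 − 15.38 = 5.30, or 53% of the drift. The day term removes the bias. Placebo rows then lower the SD of the estimate from 0.46–0.48 to 0.41–0.43. A separate run with no true effect gave 5.36, 5.36, 0.02 and 0.04 for the same four fits.

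**5. Sensitivity to the assumptions.** Inputs varied: drift 10 or 20 points rising linearly to Week 12, true Emax 0 or 60, EC50 50–300 ng/mL, elimination rate 0.15 or 0.4 per hour, residual SD 10, troughs included. Share of drift credited to drug:

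| Fit | Share |
|---|---|
| Active arms, pooled, no time term | 48–58% |
| Active arms, Week 12 alone, no time term | 95–113% |
| Active arms, pooled, time term | −3% to +4% |
| All arms, pooled, time term | −2% to +2% |

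**The case against.** A reader might infer that the set definition itself causes the bias. Steps 2 and 4 show that it does not: restoring placebo at zero concentration without a drift term changes no estimate, and a day term on the active arms alone corrects the pooled fit. That part of the case for leaving the set alone stands. Its limit is that the active-only correction works here because the simulated curve has the same Emax form as the fitted one. With real data, separating a common shift from drug effect in the active arms relies on that form. If Week 12 is fitted alone, the intercept is an extrapolation to zero concentration, with no drug-free record to support it.

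Three further objections carry weight.
- SAP Section 12 gives no equation, so it neither states nor rules out a drift term. It is fair to call this under-specification. The exclusion of placebo, by contrast, is explicit.
- Placebo PD data are not ignored. SAP 11.2 and 11.3 summarise them by treatment and day, so a placebo shift would be visible beside the model. Those summaries do not enter the fit.
- The endpoint is exploratory, the protocol makes the modelling optional, and no decision rule hangs on it. Six placebo subjects is also a target and not a guarantee.

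**Conclusion.** The point holds as a minor improvement. Placebo subjects are excluded from the PK/PD set, and the stated model has no term for non-drug change. If such change occurs, part of it is reported as drug effect: about half with days pooled, nearly all with Week 12 fitted alone. The SAP does not say which fit applies.

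The documents do not support saying that all of the change is credited to drug whatever the fit, or that a bias of known size exists. No non-drug drift in basophil activation is reported anywhere in them. Drift, residual SD, Emax, EC50 and elimination rate in the working are assumptions. Nor does the point reach the primary efficacy or safety results, which do not use this model.

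What placebo data would add is narrower: a drift estimate that does not depend on the assumed Emax shape, a little precision, and the only direct anchor if Week 12 is fitted alone.

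**What to change.** - **SAP Section 12:** write out the model with an E0-by-day term (Day 1 versus Week 12), and carry the term into the fixed-Emax and linear fallbacks. State whether days are pooled. If the Week 2, 4 and 8 predose samples are used, say how the term covers them.
- **SAP 4.5 and Protocol 7.5:** extend the PK/PD set to PD-set subjects who received placebo, with concentration set to zero, so that they inform the E0 term. SAP 10.1 already treats values below the quantification limit as zero. If the protocol is not amended, record the change in SAP Section 14, which now lists none.
- **Plots:** show the placebo points in the Section 12 scatter plots.

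The set change and the model term belong together, since the set change alone alters no Emax estimate. The cost is wording and minor programming before database lock, with no new samples or subjects.

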4.6. Imputation of Incomplete Medication Date

For the purpose of inclusion in prior and/or concomitant medication tables, incomplete medication start and stop dates will be imputed as follows:

Missing start dates (where UK, UKN and UNKN indicate unknown or missing day, month and year respectively):

- UK-MMM-YYYY:
 - If the month and year are different from the month and year of the first dose of study drug, assume 01-MMM-YYYY.
 - If the month and year are the same as the first dose of study drug month and year and the end date (after any imputation) is on or after the first dose of study drug, then assume the date of the first dose of study drug.
 - If the month and year are the same as the first dose of study drug month and year and the end date (after any imputation) is prior to the first dose of study drug, then assume the end date for the start date;
- DD-UKN-YYYY/UK-UKN-YYYY:
 - If the year is different from the year of the first dose of study drug, assume 01-JAN-YYYY of the collected year.

- If the year is the same as the first dose of study drug year and the end date (after any imputation) is on or after the first dose of study drug, then assume the date of the first dose of study drug.
- If the year is the same as the first dose of study drug and the end date (after any imputation) is prior to the first dose of study drug, then assume the end date for the start date.

Missing stop dates (where UK, UKN and UNKN indicate unknown or missing day, month and year respectively):

- UK-MMM-YYYY: Assume the last day of the month;
- DD-UKN-YYYY/UK-UKN-YYYY: Assume 31-DEC-YYYY.

If start date is completely missing and end date is not prior to the first dose, then the medication will be classified as concomitant. If the start date is completely missing and the end date is prior to the first dose of study drug, then the medication will be classified as prior. If the end date is completely missing, then the medication will be classified as concomitant. Medications for which both the start and end dates are completely missing will be classified as prior and concomitant.

5. Subject Disposition

5.1. Disposition

The number of subjects screened, the number and percentage of subjects randomized and not randomized among all subjects screened, and the violated eligibility criteria will be summarized. The above percentages will be calculated using the number of subjects screened as the denominator.

The number and percentage of subjects included in the ITT set, mITT set, PP set, and Safety set will be summarized by treatment group. The percentages will be based on the number of subjects randomized.

The number and percentage of subjects who entered, completed and discontinued the treatment period, and the number and percentage of primary reasons for discontinuation of treatment will be provided by treatment group and overall. The primary reasons for discontinuation will be summarized as collected on the disposition CRF page. Repeat the summary for study completion/discontinuation.

The number and percentage of subjects by region, study site and treatment group will be tabulated based on ITT set.

Listings for subject eligibility/analysis set and listings for subject treatment will be provided.

5.2. Protocol Deviations

The protocol deviations/violations will be identified and assessed by clinical research physician or designee following institution standard operational procedures. Any major protocol deviation/violation will be assessed prior to the final database lock, and to be considered for exclusion from Per-protocol Set.

The protocol deviations/violations will be summarized by significance and treatment group and overall based on the ITT set. If there are any deviations caused by COVID-19 pandemic, a separated summary for these specific deviations will be provided as well.

A listing of subjects with protocol deviations/violations will be provided with detail protocol deviation category and description presented.

6. Demographics and Baseline Characteristics

The demographics and baseline characteristics will be summarized by treatment group and overall based on the ITT set. No inferential statistics will be presented. Individual subject listings will be provided to support the summary tables.

6.1. Demographics

The following characteristics will be summarized:

- Age (years)
- Age category (<65, \geq 65 to <75, \geq 75)
- Sex (Male, Female)
- Race (African American, American Indian or Alaska Native, Asian, Native Hawaiian or other Pacific Islander, White, Other)
- Geographic region (APAC, EMEA, NA)
- Height (cm) and Weight (kg)
- Body mass index (BMI; kg/m²), calculated as BMI (kg/m²) = baseline weight (in kilograms) / height² (in meters).
- Time since RA onset (in years), calculated as date of (informed consent – date of RA diagnosis + 1) / 365.25. If either month or month and day of RA diagnosis date is missing, use the January 1. If day is missing, use the first day of the month. Imputation will not be done for completely missing date.

6.2. Baseline Disease Characteristics

Variables indicated below will be summarized descriptively:

- Number of previous csDMARDs treatment
- Previous csDMARDs treatment category (0-2, \geq 3)
- Number of previous anti-TNF biologic agents use
- Previous anti-TNF biologic agents use (Yes, No)
- Baseline DAS28-hsCRP (based on 3 individual components including TJC, SJC and hsCRP)
- Baseline tender joint count based on 28 joints (TJC28)
- Baseline swollen joint count based on 28 joints (SJC28)
- Baseline HAQ-DI total score
- Baseline physician global assessment of disease activity (VAS)
- Baseline subject global assessment of disease activity (VAS)
- Baseline subject assessment of arthritis pain (VAS)

- Baseline hsCRP (mg/L)

The number of previous csDMARDs treatment is calculated as the number of unique medications that were captured in the eCRF page Prior and Ongoing RA Treatments and limited to the following standardized medication list: Methotrexate, Sulfasalazine, Hydroxychloroquine, Minocycline, Leflunomide, Hydroxychloroquine sulfate, Methotrexate sodium.

The number of previous anti-TNF biologic agents is calculated as the number of unique medications that were captured in the eCRF page Prior and Ongoing RA Treatments and limited to the following standardized medication list: Adalimumab, Etanercept, Infliximab, Certolizumab Pegol, Golimumab.

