6.3.1 Disease Activity Score Using 28 Joint Counts

Disease activity score using 28 joint counts (hsCRP) will be evaluated prior to randomization at Visit 1 and at each subsequent visit.

The core set of variables for DAS28 for this study include:

- Number of tender and swollen joints with a total of 28 joints assessed for tenderness and 28 for swelling (Appendix 13.5)
- Subject's global assessment of disease activity (VAS) (Appendix 13.8)
- hsCRP

Note: During the Protocol Amendment 2 dated 08 Feb 2019, the subject's global assessment of disease activity VAS scale was reversed from the standard way they are presented in clinical trials. Scoring of this VAS scale was found to be variable across the sites, since some sites used the reverse scales, while others used the original anchors. Given this inherent

variability, the primary endpoint will now include only the 3 component DAS28-hsCRP, excluding the global assessment of disease activity VAS.

DAS28 based on CRP (DAS28-CRP) may be calculated using 3 or 4 variables.

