8.1.4. Subject Assessment of Arthritis Pain (VAS)

Per protocol version 3.0 (dated 08Feb2019), the subject is asked to measure his/her arthritis pain by marking a vertical tick on a 100mm horizontal line, where left end (0 mm) represents extreme pain and the right end (100 mm) represents no pain. Starting from protocol version 4.0 (dated 03Apr2020), the subject will be asked to measure his/her arthritis pain by marking a vertical tick on a 100mm horizontal line, where the left end (0 mm) represents no pain and the right end (100 mm) represents extreme pain. The visit and visit date when the subject started or switched to the correct scale described in protocol version 4.0 will be captured in eCRF page Corrected VAS Pain Scale.

Due to the VAS scale was reversed from the standard way they are presented in the clinical trial during protocol version 3.0 (dated 08Feb2019), scoring of the VAS scale was found to be variable across the sites. The clinical team will determine on a subject by subject basis how the subject assessment of arthritis pain was scored and identify subjects who completed consistently the subject assessment of arthritis pain throughout the study to be included in the relevant sensitivity analyses. The detail of subjects who will be included for the relevant sensitivity analyses will be provided in a separate document and will be reviewed and finalized by sponsor prior to the final database lock.

The arthritis pain scores to be used in the analysis will be the length from the anchor of no pain to the vertical tick marked by the subject, which is the number reported on eCRF using the correct scale and the value of 100 minus the number reported using the reversed scale.

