8.3. Secondary Efficacy Endpoints

8.3.1. Primary Analysis

The primary analysis will be conducted on observed cases without any imputation. All the secondary efficacy endpoints will be summarized and analyzed by treatment group at each schedule visit (Week 2, 4, 8, and 12) based on the ITT set and then repeated on the PP set.

The DAS28-related secondary endpoint is based on 3 individual components including TJC28, SJC28 and hsCRP (see calculation in [Section 8.1.1](#)). The analyses on ACR responses (ACR20, ACR50 and ACR70) will be restricted to subjects who completed subject global assessment of disease activity consistently, as well as physician global assessment of disease activity and subject assessment of arthritis pain, using the same approach as the sensitivity analysis on 4-component DAS28-hsCRP to identify the subjects to be included in the analysis. Similar to the

analyses on ACR responses, the analyses on the individual component using VAS will be restricted to subjects who completed the corresponding individual VAS assessment.

Frequency counts and percentages will be provided for ACR responses (ACR20, ACR50, and ACR70) at each schedule visit. The Chi-square tests will be used to compare the ACR response rate between each of active treatment group and placebo group, and among active treatment groups at each schedule visit. The p-values from the Chi-square tests will be presented. In case of few responders where Chi-square test may not be appropriate or accurate, Fisher's exact test will be performed instead. Besides, 95% CI of binomial proportion of ACR response within each treatment group and 95% CI of the difference in proportion of subjects with ACR response for pairwise treatment comparison will be estimated using the Wald method.

The hsCRP will be summarized descriptively by treatment group over schedule visits. No inferential statistics will be provided.

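### SAP 6.2 tabulates baseline VAS scores on the whole ITT set without converting by the scale used, so physician and subject global readings made on the original anchors would enter reversed

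*SAP*

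**What the plan says.** The opening paragraph of SAP Section 6 sets the population: "The demographics and baseline characteristics will be summarized by treatment group and overall based on the ITT set". It adds that no inferential statistics will be presented. SAP 6.2 then lists the variables, including "Baseline physician global assessment of disease activity (VAS", "Baseline subject global assessment of disease activity (VAS" and "Baseline subject assessment of arthritis pain (VAS". None of the three carries a restriction, a conversion rule or a reference to SAP 8.1.4 or 8.1.5.

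Protocol 6.3.1 records that scoring of the subject global scale varied, "since some sites used the reverse scales, while others used the original anchors", and takes that component out of the primary endpoint for this reason. SAP 8.1.4 and 8.1.5 report variable scoring across sites for pain and for both global scales.

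The conversion rules differ by scale:
- **Pain (SAP 8.1.4).** The score depends on the form used, "which is the number reported on eCRF using the correct scale and the value of 100 minus the number reported using the reversed scale". An eCRF page records the visit and date at which the subject started on, or switched to, the corrected form.
- **Physician and subject global (SAP 8.1.5).** One orientation is described (0 = not well, 100 = very well), and every reported value is subtracted from 100.

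For efficacy, SAP 8.3.1 says that "the analyses on the individual component using VAS will be restricted to subjects who completed the corresponding individual VAS assessment". SAP 8.2.5, 8.3.2 and 8.5 limit the 4-component DAS28, ACR and VAS subgroup analyses to subjects who completed the relevant scale consistently. A separate document, finalised before database lock, will list those subjects.

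**The concern.** The exclusion of inconsistent subjects is the only stated protection against global readings taken on the other form, and SAP 6.2 does not invoke it. Followed as written, the plan gives baseline means and SDs for the physician and subject global scales in which some values may run opposite to the rest.

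Readers use the baseline table to judge disease severity and comparability of the arms. A row that mixes directions understates severity, overstates spread and adds arm differences that come from the form used rather than from the patients. The report would also carry two baseline means for the same VAS, one on the ITT set and one on the restricted subset, with nothing to explain why they differ.

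**Working it through.** The plan states no figure for these rows, so there is none to reproduce. The check has two parts.

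**1. Does a stated rule put each row in one direction?**

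- *Global scales.* SAP 8.1.1 needs the subject global with 0 = very well and 100 = not well. SAP 8.1.5 describes the form with the ends the other way round and subtracts from 100. A reading x on that form becomes 100 − x, which is right. I take the original anchors in Protocol 6.3.1 to be the standard form (0 = very well). A reading x on that form is already in the right direction, and 100 − x reverses it. Protocol 6.3.1 is narrower than SAP 8.1.5: it applies the subtraction to included subjects who used the reversed scale. The uniform rule does no harm in a subset that used only the reversed form. SAP 6.2 is not limited to such a subset.
- *Evidence for each global scale.* The statement that sites used different anchors concerns the subject global. For the physician global, the evidence is the report of variable scoring in SAP 8.1.5.
- *Pain.* Conversion follows the form used, and the switch is recorded. The row is sound if that rule is applied to SAP 6.2 and the form is correctly recorded.

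**2. How large could the effect be?**

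Inputs: true mean m and SD s, with higher = worse, and share f of readings entered the wrong way. All are assumed; none is in the documents. The 37 per arm is from SAP 4.3.

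- Pooled mean = m(1 − f) + (100 − m)f
- Pooled SD = √[s² + f(1 − f)(2m − 100)²]
- SD of the arm difference caused by reversal alone = (2m − 100)·√[2f(1 − f)/37]

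With m = 65 and s = 18:

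| f | Pooled mean (mm) | Pooled SD (mm) | SD of arm difference from reversal (mm) |
|---|---|---|---|
| 10% | 65×0.9 + 35×0.1 = 62 | √(324 + 81) = 20.1 | 30×√(0.18/37) = 2.1 |
| 20% | 65×0.8 + 35×0.2 = 59 | √(324 + 144) = 21.6 | 30×√(0.32/37) = 2.8 |
| 30% | 65×0.7 + 35×0.3 = 56 | √(324 + 189) = 22.6 | 30×√(0.42/37) = 3.2 |

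Sensitivity to the assumptions:
- m = 60: the mean falls to 58–54 over the same shares.
- m = 70: the mean falls to 66–58, and the reversal SD is 2.8–4.3 mm.
- s = 20 with m = 65: the means are unchanged and the SDs are 21.9–24.3.
- f = 50%: the mean is 50 mm whatever the true mean.

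For scale, ordinary sampling variation in an arm difference is 18×√(2/37) = 4.2 mm. Adding reversal gives √(4.2² + 2.1²) = 4.7 mm to √(4.2² + 3.2²) = 5.3 mm.

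If SAP 6.2 were programmed on raw values with no conversion, the same formulas would hold, with f the share recorded on the reversed form.

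**The case against.** A reader might infer that all three rows pool opposite directions. The documents do not support that for pain: SAP 8.1.4 converts by the form used and records the switch. The residual risk is that the rule is not carried into SAP 6.2, or that the form is unknown or misrecorded.

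A reader might also infer that every subject left off the consistent list has a wrong baseline. That does not follow. The list concerns consistency throughout the study, whereas a baseline row uses one reading. A subject who changed form later may have a Day 1 reading of known direction, and removing all such subjects would discard usable data.

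It can be said, too, that a matching baseline is already planned. SAP 8.3.1 gives baseline descriptive statistics by arm for these endpoints within the restricted subjects, and the opening of SAP 8 includes only subjects with both values in each post-baseline summary. This largely answers any complaint that the analysed subset has no baseline of its own. An ITT-wide baseline table beside subset efficacy tables is normal practice.

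Finally, the consequences are limited. On the assumptions above at a mean of 65 mm, the arm difference from reversal is smaller than sampling variation. TJC28, SJC28, hsCRP, HAQ-DI and 3-component DAS28 in the same table are unaffected. The primary ANCOVA has baseline 3-component DAS28 as its only covariate.

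All of this stands and limits the point. It does not remove the problem for the two global rows, where the stated conversion ignores the form used and no exclusion applies.

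**Conclusion.** The point holds for baseline physician and subject global VAS. As written, SAP 8.1.5 would reverse any reading made on the original anchors, and SAP 6.2 would keep it. The bias is toward 50 mm with an inflated SD: roughly 3 to 9 mm in the mean for 10% to 30% of readings, if the true mean is 65 mm. It rests on the unstated share of such readings and on an assumed mean and SD; if no such readings exist, there is no error. For pain the point is conditional.

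A reader should not conclude that the rows are certainly wrong, that arm comparability cannot be judged, or that the primary result is at risk. The table is descriptive and the primary endpoint contains no VAS. This is a minor point, worth correcting because the correction is cheap.

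**What to change.** State in SAP 6.2 that:

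1. the three VAS rows use direction-corrected scores, converted by the scale actually used at baseline (for pain, by reference to SAP 8.1.4; for the global scales, by a rule that depends on the form instead of the uniform subtraction in SAP 8.1.5);
2. each row includes only readings whose baseline direction is established in the pre-lock subject-level review or, failing that, only subjects on the finalised consistent list for that VAS;
3. n is shown per arm for each row.

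The cost is a few lines of SAP text and the use of a review already planned. The downside is a lower n in these rows, and more so under the fallback, which can drop valid Day 1 readings from subjects who changed form later. Extra baseline columns for the consistent subset are optional. If they are added, the subset must be defined, because eligibility is set separately for each VAS and the ACR analyses need all three. No efficacy analysis has to change.
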